Hormonal and surgical steps in the transition can have reversible as well as irreversible effects on the fertility of transgender individuals. The advice of the World Professional Association for Transgender Health (WPATH) guideline is to counsel everyone about this, even if there is currently no desire for fertility preservation, for example, in adolescents(1). In the Knowledge and Care Center for Gender Dysphoria (KZcG), since 2021, we have established a protocol where all adolescents with gender dysphoria who start puberty suppression or cross-sex hormone therapy are counseled about the effects of treatment on their fertility and the possibilities for fertility preservation.

The number of adolescents with gender dysphoria seeking care at the Knowledge and Care Center for Gender Dysphoria (KZcG) has been increasing annually (Figure 1). As a result, we are seeing a larger group of adolescents in our clinic to discuss fertility preservation. Part of them assigned male at birth (i.e. transfeminine). The rise in number of adolescents is similar to other countries across the world, for example, in Australia(4).

[figure not shown]

Figure 1: Number of registrations per year of children and adolescents at the KZcG

For this group, it is particularly important to provide fertility counseling before starting puberty blockers. Because, puberty

blockers prevent or stop the production of testosterone, thereby inhibiting the development of secondary sexual characteristics. As a consequence, this also prevents or greatly reduces spermatogenesis, (i.e. the maturation of sperm cells).

From Tanner stage 2, adolescents in our center become eligible for puberty suppression. However, spermatogenesis may not have started in everyone by that stage. It is often not possible to obtain mature sperm cells from ejaculation due to both the physical and mental inability to induce ejaculation, caused by dysphoria and age. Therefore, the option of cryopreserving ejaculated spermatozoa (semen cryopreservation) is often not available.

For individuals unable to ejaculate, testicular sperm extraction (TESE) is offered. In this procedure, tissue is taken from the testes through biopsies, with the aim of finding mature sperm cells in the laboratory and freezing them for future use. The care for transgender adolescents was established in 2021 at Amsterdam UMC, location AMC.

Since 2014, in the Netherlands, the moratorium that prohibited the use of surgically obtained sperm for achieving pregnancy, which had been in effect since 1996, was lifted after the publication of the results of the study titled "ICSI with testicular sperm in men with azoospermia: an observational study with follow-up of children" conducted by Radboud UMC and Amsterdam UMC (5, 6). These studies demonstrated the safety of testicular sperm extraction (TESE) by monitoring pregnancies and children born through ICSI with testicular sperm. Since then, quality standards have been established, and the TESE procedure has been recognized and deemed safe. It has since become a standard clinical practice in specialized centers and can be used, among other cases, for fertility preservation in men with (testicular) cancer, Klinefelter patients without current desire for children, or trans women with azoospermia.

Furthermore, there is a significant amount of expertise in taking testicular biopsies in adolescents, particularly in the context of pre- and peripubertal oncology patients undergoing infertility-inducing treatments like chemotherapy. Since 2011, small pieces of testicular tissue have been frozen before the start of the treatment in these patients, allowing for the potential isolation and multiplication of stem cells from the frozen tissue in the future, to be reintroduced into the testes to fulfill the desire for children through natural conception (7). The operative risks associated with this procedure, such as infection and bleeding, are low, ranging from 1.3% to 2.6% (8). Additionally, no long-term negative effects have been observed in this group (9, 10). However, for transfeminine adolescents, this technique cannot be offered at present due to the need for testosterone replacement, which is suppressed in trans women through testosterone blockers and gender-affirming female hormones, or due to prior gonadectomy. Therefore, for the prepubertal execution of the TESE procedure, successful in vitro spermatogenesis must first be developed.

To maximize the chances of a successful TESE, spermatogenesis should already be underway, for which the production of testosterone is crucial. However, testosterone is also responsible for (irreversible) virilization, such as deepening of the voice and facial hair growth. Therefore, it is highly burdensome for this group of patients to postpone puberty suppression in order to secure their fertility for the future, especially considering that active fertility desire does not exist at the start of puberty.

Currently, there is a lack of valid clinical factors to predict when spermatogenesis has sufficiently progressed in transfeminine adolescents. The intratesticular testosterone level is significantly higher than the peripheral blood testosterone level, and the blood testosterone value is not determinative of the intratesticular level. Ideally, a high intratesticular testosterone level would be beneficial for

sperm production, while maintaining the lowest possible peripheral testosterone level to minimize virilization.

In the current clinical practice, the child endocrinologist determines the Tanner stage before initiating puberty suppression, followed by fertility counseling with the gynecologist. If fertility preservation is desired afterward, a referral to the andrologist is made to assess the indication for TESE and determine the optimal timing for the procedure. In cases where ejaculation is not possible, the andrologist uses ultrasound measurements of testicular volume, serum testosterone, LH, and FSH levels to make this determination. Recent Australian research in transfeminine adolescents has shown that testicular volume appears to be the most predictive factor. This finding is based on a retrospective cohort study with a small sample size of N=31 (11).

If the TESE procedure is performed too early, it is possible that no or insufficient suitable sperm cells can be found. TESE is an invasive procedure that can have complications such as infection and bleeding, although the chances of these complications are low. However, complications may occur even without freezing sperm cells. Additionally, it should be noted that the patient is constantly reminded of their genitalia during the postoperative period, which can cause dysphoria. The procedure should be performed in a way that avoids permanent damage to the testes, ensuring that the process is reversible in case the patients choose their assigned gender at birth or if there is sufficient tissue available to assess the presence of sperm cells at the time of gonadectomy.

Puberty progresses differently in each individual. In some cases, secondary changes occur faster than sperm maturation, leading to high levels of mental distress due to dysphoria, which may cause patients to refrain from undergoing TESE. This period can also be stressful and uncertain for both the child and the parents. Therefore, it

| | |
|-------------------------|---|
| | 
is important to provide comprehensive counseling and multidisciplinary support throughout the process.
 
Currently, there are no ideal clinical non-invasive parameters to determine the optimal timing for TESE. To determine the appropriate moment for a successful TESE there is need to set up a cohort study of all transfeminine adolescents who are referred for TESE. This will enable us to make better predictions in the future and optimize our fertility counseling and care.
 
Furthermore, we intend to improve the counseling and support provided to both parents and the child by examining the experiences of the referred group throughout the entire process and reflecting on the experiences of the group that has undergone TESE.
 |
| Objective | 
When is the TESE process most successful by:
 
 1. Identifying clinical non-invasive parameters that indicate a high likelihood of finding mature sperm cells. 2. Evaluating the experience of the process for patients and parents to determine the potential physical and emotional burden of the TESE process and identifying factors that can reduce this burden to improve feasibility. |
| Study design | 
For part 1 of the research question "when is the sperm yield from TESE most successful," the study design is observational, including both retrospective and prospective cohort research, utilizing data from medical records.
 
To address the second part of the research question, we intend to employ a descriptive research method. This will involve qualitative research through interviews and quantitative research through questionnaires administered to both the children and their parents during or after the treatment.
 |
| Study population | 
Healthy adolescents assigned male at birth with gender dysphoria and a desire for surgical fertility preservation prior to or after the
 |

| | |
|------------------------------------|--|
| | temporary discontinuation of puberty suppression, who have been referred to the andrologist |
| Inclusion criteria | 
Patients will be included if they meet the following criteria:
 
 • (Parents of) Individuals assigned male at birth who identify as transfeminine (trans girl, non-binary person, etc.). • Under the care of a specialized gender center or clinic • Have a diagnosis of gender dysphoria according to the Diagnostic and Statistical Manual of Mental Disorders, Fifth Edition (DSM-5) or a diagnosis of gender incongruence according to the International Classification of Diseases, 11th Revision (ICD-11). • Have not yet started or have discontinued puberty suppression before the start of gender affirming hormone treatment. • Referred or scheduled for referral to the andrologist following fertility counseling. |
| Exclusion criteria | Patients will be excluded if they do not wish to participate in this research. |
| Sample size | We aim to conduct the study over a period of 2 years to include a sufficient number of 30-40 adolescents, allowing us to generate valid data. |
| Recruitment of participants | 
The participants who have already undergone TESE will be approached by the primary treating physician during their clinic visit or via telephone. The participant information will then be sent to them via email or mail. During the next physical appointment that the participant has at gender clinic, the consent form will be signed in the presence of the researcher.
 
If the referral has not yet been made, the primary treating physician will inform the participant about the study during the fertility counseling session and provide them with the participant information after the consultation. If a referral for TESE is desired, the primary treating physician will contact the participants and their parents by phone to confirm their interest in participation. A one-week
 |

| | |
|---|---|
| | consideration period will then begin. If participation is desired, the consent form will be signed during the next physical appointment in the presence of the researcher. If the participant has a long distance to travel to the gender clinic and does not have any upcoming physical appointments in the near future, the consent form will be sent by mail with a prepaid return envelope. |
| Intervention | The participant information will include a request for permission to use data from the medical records for scientific research purposes. For the second part of the research question, we will also inquire whether the participant and their parents are willing to complete a questionnaire at least once and up to three times, with each questionnaire taking a maximum of 10 to 15 minutes. Additionally, a minimum of 5 study participants who have undergone TESE will be asked to participate in an interview, as well as their parents. Similarly, a minimum of 5 study participants who are referred to the andrologist will also be invited to participate in an interview, along with their parents. The interviews will take place once at location or via video call if there is a long travel distance, and they will last a maximum of 1 hour. |
| Standard care / Standard treatment | All adolescents are referred for fertility counseling before starting puberty suppressants. In this consultation, a counseling session takes place regarding fertility preservation. If the patient expresses a desire for preservation and is eligible for TESE (due to age/early puberty/incapacity to produce ejaculation), they are referred to the andrologist. An intake appointment is scheduled, after which the indication for TESE is confirmed. Currently, the indication is based on blood values (testosterone, LH, FSH) and an ultrasound to determine testicular volume. If the testicular volume or laboratory values are still insufficiently indicative of a successful TESE, the examination is repeated after 3 to 6 months or upon the patient's request if puberty progresses more rapidly and intensely than expected, thus tailored to the patient. The TESE procedure is performed in an outpatient setting under general anesthesia with local anesthesia, using microsurgery |

| | |
|-----------------------------|---|
| | techniques to obtain small pieces of testicular tissue, ensuring reversibility of the procedure. |
| Study parameters | 
Primary outcome measures:
 
Part 1:
 
Ultrasound-determined testicular volumes before TESE procedure, when this is not available, we will use the measurements of the Tanner stage at the time of the procedure, by the pediatric endocrinologist.
 
Laboratory values (testosterone, LH, FSH) shortest before the TESE procedure, including subsequent measurements, collected as part of routine clinical care for non-study purposes
 
Age at the time of TESE
 
Presence of spermatozoa
 
Number of cryopreserved straws
 
Quality of obtained sperm cells (concentration/motility)
 
Part 2:
 
Experience of the TESE procedure for the patient and parents
 
Experience of counseling for the patient and parents
 
Experience of any waiting period for the patient and parents
 
Feasibility for adolescents: Outcome of TESE after referral (whether the TESE procedure was carried out or not)
 |
| Study endpoints | 
Secondary outcome measures:
 
Progression of secondary sexual characteristics/virilization from the time of referral to the TESE procedure
 
Subgroup of patients who temporarily discontinued puberty suppressants
 |
| Statistical analysis | 
The statistical program SPSS will be used for analyzing the observational cohort and questionnaires.
 
Descriptive analyses will be conducted to display the central tendency (mean, median, and mode) and variation (range and standard deviation) of the included sample.
 |

| | |
|--|---|
| | 
To demonstrate a statistically significant relationship between different variables and the observed outcomes, linear and multivariate regression analyses will be employed. If necessary, adjustments will be made for confounding factors.
 
The questionnaires will be sent via Castor and analyzed using SPSS.
 
The interviews will be transcribed verbatim. Transcripts will be coded using the MaxQDA software program, from which thematic analysis themes will be derived.
 |
| Burden for the participant | 
The interviews are conducted face-to-face or, in the case of long travel distances, through video consultations. The interviews last for a single session of 45-60 minutes. The questionnaires are sent online and take approximately 15 to 20 minutes to complete. The topics of fertility and the physical changes related to the TESE procedure discussed in the interviews can be considered intimate information. However, it is important to note that these topics are also routinely discussed by physicians and psychologists during clinical visits. Therefore, participants may find it relatively normal to discuss these topics with their healthcare providers. Nevertheless, participants have the option to select "I do not want to complete this questionnaire" for each questionnaire, in which case the questions will be removed from the digital survey. Apart from the time invested in completing the questionnaires and/or participating in interviews, there is no additional burden on the participants. Blood tests are always part of the treatment process and there are no additional blood sampling moments.
 |
| Risk for the participant | The participant faces no risks. |
| Benefits of participating in the research | The participant does not have direct benefits from participating in the research. Indirect benefits may include the potential improvement of care and information provision within the Knowledge and Care Center for Gender Dysphoria, both nationally and internationally, based on the research outcomes. This can be perceived as highly meaningful. |

| | |
|---|---|
| Disadvantages of participating in the research | The participant has no disadvantages of participating in the research. |
| Compensation for the participant | The participant will not receive any compensation for participating in the research. |
| Administrative aspects | 
The patient characteristics and treatment details (success, outcomes, etc.) will be collected from the medical records and stored in a pseudonymized SPSS file, which is password-protected. The database is stored on a secured departmental drive and is accessible only to the authorized researchers. Access to the database is monitored and recorded. The questionnaires will be administered using Castor EDC Surveys. This ensures that all data is stored in an encrypted format.
 
The research data and the resulting database will be retained for up to 15 years after the completion of the study and will then be destroyed.
 |

2. de Vries AL, Steensma TD, Doreleijers TA, Cohen-Kettenis PT. Puberty suppression in adolescents with gender identity disorder: a prospective follow-up study. *J Sex Med*. 2011;8(8):2276-83.
3. de Vries AL, McGuire JK, Steensma TD, Wagenaar EC, Doreleijers TA, Cohen-Kettenis PT. Young adult psychological outcome after puberty suppression and gender reassignment. *Pediatrics*. 2014;134(4):696-704.
4. Pang KC, de Graaf NM, Chew D, Hoq M, Keith DR, Carmichael P, Steensma TD. Association of Media Coverage of Transgender and Gender Diverse Issues With Rates of Referral of Transgender Children and Adolescents to Specialist Gender Clinics in the UK and Australia. *Jama Network Open*. 2020;3(7).

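### The recruitment text gives no way to approach adolescents already referred who have not had TESE, although the cohort is meant to cover all referred

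*Protocol*

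**What the plan says.** All references are to the protocol.

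- **Recruitment of participants** describes two groups. The first: "The participants who have already undergone TESE will be approached by the primary treating physician during their clinic visit or via telephone". The second: "If the referral has not yet been made, the primary treating physician will inform the participant about the study", at the counselling session, followed by a telephone call if a referral is wanted. The remaining sentences, on the week for consideration and on signing or posting the consent form, follow from the second route and open no third one.
- **Background** states the aim: "there is need to set up a cohort study of all transfeminine adolescents who are referred for TESE". It also sets two groups side by side for the experience research: "examining the experiences of the referred group throughout the entire process and reflecting on the experiences of the group that has undergone TESE".
- **Study population and Inclusion criteria** ask for referral, or planned referral, to the andrologist. Having had TESE is not required.
- **Study parameters, Part 2** lists as primary measures the experience of any waiting period and a feasibility measure: whether or not TESE took place after referral.
- **Study design** says that questionnaires are "administered to both the children and their parents during or after the treatment".
- **Intervention** plans interviews with at least 5 participants who had TESE and adds: "Similarly, a minimum of 5 study participants who are referred to the andrologist will also be invited to participate in an interview".

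**The concern.** Recruitment as described is narrower than the population the protocol defines, and the missing part is not random. Among adolescents referred before they could be told of the study at counselling, the described way in is to have had TESE. That is the very event the feasibility measure records.

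Two Part 2 results are exposed. Feasibility can look better than it is if participants selected on a positive outcome are counted. The experience data can also lack past patients who stopped before TESE. The background expects such patients, because puberty may advance faster than sperm maturation, "leading to high levels of mental distress due to dysphoria, which may cause patients to refrain from undergoing TESE". Objective 2 sets out to measure the burden of the process, and those who stopped because of it are the most informative on that question. A later analysis plan can choose a denominator, but it cannot recover people who were never approached.

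**Working it through.** The protocol has no figure to reproduce here. The check sets the sections side by side, then uses a short formula for direction only.

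**1. Status when recruitment opens, against the recruitment text**

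| Status | Meets the referral criterion | Way in described |
|---|---|---|
| A. TESE done | yes | yes, visit or telephone |
| B. Referred, waiting, later has TESE | yes | none while waiting; can enter as A afterwards, since no cut-off date is set |
| C. Referred, never has TESE | yes | none |
| D. Not yet referred | yes, once referral is planned | yes, at counselling |

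The gap is C, and B for as long as they wait. For B the experience of waiting is then recalled, not recorded as it happens. D can go on to wait or refrain and is captured prospectively.

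**2. Can B and C exist?** The background says that "since 2021, we have established a protocol where all adolescents with gender dysphoria who start puberty suppression" or cross-sex hormones receive fertility counselling, so referrals can predate the study. The Standard care section has examinations repeated after 3 to 6 months when the findings do not yet favour TESE, which creates waiting. The background expects some to refrain. No section gives a count.

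**3. Effect on the feasibility measure.** Let r be the share of participants recruited because TESE was done, and u the share of referrals in which TESE takes place. Neither is in the protocol, so both are assumptions.

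- Completion among those recruited after TESE = 1 by construction, whatever u is. They carry no information on u.
- If they are pooled with the rest: observed proportion = r + (1 − r)u.
- Bias = r + (1 − r)u − u = r(1 − u), which is never negative.
- Example at r = 0.5, u = 0.7 and N = 40 (the top of the planned 30–40): 20 + 0.7 × 20 = 34, and 34/40 = 85%, against 14/20 = 70% in those enrolled at or before referral. Difference: 15 points.
- Over r = 0.25 to 0.75 and u = 0.6 to 0.8: from 0.25 × 0.2 = 5 points to 0.75 × 0.4 = 30 points.

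These values show the direction and how the bias depends on r and u. They do not estimate its size in this study.

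**4. Do those recruited after TESE enter Part 2?** Yes. Questionnaires may be given after treatment, and at least 5 who had TESE are interviewed. Whether they also enter a feasibility proportion is not stated.

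**5. Part 1.** Sperm yield can be observed only after TESE, so the gap does not bias it.

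**6. Eligibility of C.** A further inclusion criterion requires that puberty suppression has not been started, or has been discontinued, before gender-affirming hormones. It gives no time point. Read at referral, past patients who refrained can qualify. Read at enrolment, those who have since started suppression may not, and the same reading would touch past TESE patients.

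**The case against.** The strongest reply is that silence is not exclusion. The recruitment section tells how two groups are informed and does not say that only these are recruited. The population is set elsewhere as those referred, and the separate interview group of referred patients shows that participants without TESE are intended. This stands in part: nothing bars approaching them. But no step does so, and the interview group can be filled entirely from those enrolled before referral.

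A second reply is that the retrospective label belongs to Part 1, and that the feasibility denominator is a matter for the analysis plan. That stands as to the denominator. It does not reach the question of whom to approach, which is settled at recruitment.

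A reader might infer more than the documents support:

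- *That everyone already waiting is lost.* Those who later have TESE can enter by the first route, and no cut-off date prevents it.
- *That feasibility will be overstated by a definite amount.* The protocol gives neither input and neither states nor excludes pooling.
- *That a given number of patients is missing.* No referral counts are given, the group could be small, and some past patients may not be eligible under the undated suppression criterion.
- *That the study will see no refrainers at all.* Those enrolled before referral can still refrain and be recorded.

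**Conclusion.** The point holds in a limited form. The recruitment text does not match the cohort the protocol defines. Followed as written, it makes entry from past referrals depend on TESE having been done, which is a Part 2 outcome. Two consequences follow: participants from past referrals tell nothing about feasibility and would bias upward any proportion that includes them; and the experience of already-referred patients who never reach TESE is not collected.

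The direction of the bias is certain if the groups are pooled. Its size is unknown. The conclusion rests on three assumptions: that recruitment follows the text, that some patients had been referred without TESE before the study could reach them at counselling, and that at least some of them meet the suppression criterion. It should be corrected, because the change is small and the loss cannot be repaired afterwards.

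**What to change.** 1. Reword the first recruitment sentence so that all eligible adolescents already referred to the andrologist, whether or not TESE followed, are approached by the primary treating physician at a clinic visit or by telephone.
2. State the time point at which the puberty-suppression inclusion criterion is assessed, so that the eligibility of this group is clear. The choice is the sponsor's.
3. Report the numbers approached and responding by TESE status.
4. Report the feasibility outcome separately for those recruited after TESE, and do not merge past refrainers into the remainder, which would tilt the figure the other way. Those enrolled at or before referral give the cleanest proportion.

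**Cost:** a few extra contacts and two sentences of protocol text. Response may be lower among those without TESE, which is the reason for item 3. Item 4 costs precision. If half the participants were recruited after TESE (an assumption), the clean proportion rests on 15 to 20 people. The Wilson 95% interval would be 41.7% to 84.8% for 10/15 (43 points wide) and 48.1% to 85.5% for 14/20 (37 points wide). Item 4 without item 1 would protect the proportion but still lose the experience of past refrainers.

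### Adolescents who already had TESE are asked for consent after the procedure and refusers are excluded, so consent that depends on the result would bias the estimated chances of finding sperm without being detected

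*Protocol*

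**What the plan says.** The Study design row describes Part 1 as "observational, including both retrospective and prospective cohort research", drawing on medical records. The Recruitment of participants row sets two routes.

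- **TESE already done.** "The participants who have already undergone TESE will be approached by the primary treating physician during their clinic visit or via telephone". Then: "During the next physical appointment that the participant has at gender clinic, the consent form will be signed in the presence of the researcher".
- **Not yet referred.** "If the referral has not yet been made, the primary treating physician will inform the participant about the study during the fertility counseling session". Consent follows at a later visit or by mail.

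Record data depend on consent. The Intervention row says "The participant information will include a request for permission to use data from the medical records for scientific research purposes", and the only exclusion criterion is "Patients will be excluded if they do not wish to participate in this research".

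The Sample size row gives a single target of 30-40 adolescents. The Statistical analysis row gives a single regression plan, with adjustment for confounding if needed. Neither distinguishes the two routes. The background text just before the Objective row says "there is need to set up a cohort study of all transfeminine adolescents who are referred for TESE", and the first objective is to find non-invasive parameters that point to a high likelihood of mature sperm.

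**The concern.** On the first route, the decision to enter the study comes after the event that Part 1 studies, the presence of spermatozoa. The treating physician who makes the approach, and probably the family, will know how the procedure turned out. If willingness to take part differs between those with and those without sperm, the enrolled group contains the wrong mix of successes and failures. Adolescents recruited before TESE cannot select themselves on a result that does not yet exist.

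The study is meant to support better predictions and counseling, so the absolute chance of finding sperm at a given testicular volume or hormone level matters as well as its association with those measures. Selection on the result distorts that absolute chance. A confidence interval would not show it. Because the protocol provides no count of refusers by result, a later analysis could not recover it either.

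**Working it through.** **The plan's own figure.** The 30-40 is given without error rate, power, effect size or precision target, so there is nothing to reproduce. The protocol also gives no retrieval rate, no consent rates and no split between routes. All of these are assumed below.

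**Inputs (assumptions).** p = true chance of finding sperm; f = share of eligible adolescents approached after TESE; c1 and c0 = consent after TESE when sperm was found and not found; cp = consent before TESE, set at 0.9.

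**Formula.** Observed rate = [f·p·c1 + (1−f)·p·cp] / [f·(p·c1 + (1−p)·c0) + (1−f)·cp].

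**Worked case.** With p = 0.5, c1 = 0.9 and c0 = 0.6, the numerator is 0.45 for every f.

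- f = 0.25: denominator 0.25×0.75 + 0.75×0.9 = 0.8625; rate 0.522
- f = 0.50: denominator 0.375 + 0.45 = 0.825; rate 0.545
- f = 1.00: denominator 0.75; rate 0.600

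The same formula for other assumptions:

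| True rate | Consent after TESE, found / not found | f = 25% | f = 50% | f = 100% |
|---|---|---|---|---|
| 50% | 90% / 60% | 52.2% | 54.5% | 60.0% |
| 50% | 90% / 70% | 51.4% | 52.9% | 56.3% |
| 50% | 60% / 90% (reversed) | 47.8% | 45.5% | 40.0% |
| 70% | 90% / 60% | 71.8% | 73.7% | 77.8% |

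With equal consent (90% / 90%) the formula returns the true rate.

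**Sampling error for comparison.** The 95% half-width at p = 0.5 is 1.96·√(0.25/n), which is 0.179 for n = 30 and 0.155 for n = 40. The shifts above, at most 10 percentage points, lie inside it. They do not fall as n grows.

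**Effect on associations.** A logistic simulation of 1,000,000 records used a true log odds ratio of 1.00, half recruited after TESE, and a wider consent gap of 90% against 50%. Route did not depend on the predictor. Predicted chances at −1, 0 and +1 SD of the predictor rose from 0.27, 0.50 and 0.73 to 0.32, 0.56 and 0.78, while the log odds ratio stayed at 1.00. When consent after a failed TESE also depended on the predictor (70% below its mean, 40% above), the log odds ratio moved to 1.10.

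**An intercept correction.** Dividing the odds by the ratio of participation fractions looks like a remedy. In the 90% / 60% case with f = 50%, the pooled odds are 0.545/0.455 = 1.2. Dividing by the post-TESE ratio 0.9/0.6 = 1.5 gives 0.8, or 44% in place of the true 50%. The fractions must cover the same patients as the model: 0.9 against 0.5×0.6 + 0.5×0.9 = 0.75, a ratio of 1.2, which restores 50%.

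**The case against.** Several objections have weight.

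- **Knowledge of the result and pooling are inferred.** The protocol does not say that the result has been disclosed when consent is sought, nor that the two groups are analysed without distinction. Both are natural readings of an approach made after TESE and of a single design, target and regression plan, but they remain inferences. A statistical analysis plan that is not shown could separate the routes. It could not recover refusers who were never counted.
- **Coverage of past procedures.** A reader might infer that the physician may choose whom to approach. The text does not support that: it says those who had TESE will be approached, gives no selection rule, and aims at all referred adolescents. What it lacks is a source list against which completeness could be checked.
- **Motive.** No document says that families decline after a failed TESE. Part 1 needs only permission to use records, and each questionnaire can be declined, so a distressed family can still contribute Part 1 data. The direction of any bias is therefore open.
- **Purpose.** The analysis text speaks of relationships between variables and names no calibrated risk model. If consent depends on the result alone, logistic odds ratios survive. The stated wish for better predictions and the objective's reference to likelihood keep absolute chances in play.

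**Conclusion.** The concern holds in conditional form. The protocol fixes consent after TESE for one group and excludes refusers, and it gives no means of seeing whether participation differs by result. If it does differ, the retrieval rate and predicted chances are biased.

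Under the 90% / 60% / 90% assumptions a true 50% appears as about 52% to 60%, depending on the share approached after TESE. With the gap reversed it appears as about 48% down to 40%. All these rates and shares are assumptions.

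Two stronger readings should be resisted. A reader might take 60% (or 78% for a true 70%) as the expected error, but those figures apply only if the whole cohort is recruited after TESE, whereas the plan has a prospective part. A reader might also conclude that every association is biased. That would need consent, or the mix of routes, to vary with the predictor as well. Actual bias has not been shown, and at 30-40 participants it would probably be smaller than the random error. The change is worth making because it is cheap and more patients would not cure the problem.

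**What to change.** - In Recruitment of participants, state that all past TESE procedures are listed from the clinic log and that every one is approached.
- Report anonymous aggregate counts of TESE with and without sperm beside those of participants, by recruitment route, if such totals may be used without consent.
- Record for each participant whether consent came before or after TESE, and repeat the Part 1 analysis in those who consented before it.
- Do not plan an intercept correction. If one is wanted, use participation fractions from the same set of patients as the model and label it exploratory, because with so few patients the ratio will be imprecise.

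The cost is one count from the log, a sentence or two on recruitment, and one sensitivity analysis that will be less precise than the main one.
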